## **8.2 Clinical laboratory data**

The following clinical laboratory parameters will be measured (see section [12.1](#)):

- At the screening visit,
- On Day 1, Week 1, Week 2, Week 4, Week 6, Week 8 (8 or 12 Week Cohorts), Week 10 (12 Week Cohorts), Week 12 (12 Week Cohorts), safety follow-up visit.

Additional measurements are done on Week 3, Week 5 and Week 7 for alanine aminotransferase (ALT) and aspartate aminotransferase.

**Haematology** parameters will be listed and grouped as follows:

- Red blood cells: haemoglobin (g/L), haemoglobin A1C (mmol/mol) only at screening, hematocrit (fraction of 1), mean corpuscular haemoglobin (MCH) (fmol), mean corpuscular

haemoglobin concentration (MCHC) (mmol/L), mean corpuscular volume (MCV) (fL), mean platelet volume (MPV) (fl), erythrocyte sedimentation rate (mm/h), red distribution width (RDW) (%), reticulocytes (G/L and %) and red blood cell count (RBC) (T/L).

- White blood cells: basophils (G/L and %), eosinophils (G/L and %), lymphocytes (G/L and %), monocytes (G/L and %), neutrophils (G/L and %) and white blood cell count (WBC) (G/L).

- Platelets (G/L).

**Blood chemistry parameters** will be listed and grouped as follows:

- Liver function: alanine aminotransferase (ALT) (IU/L), alkaline phosphatase (IU/L), aspartate aminotransferase (AST) (IU/L), total bilirubin ( $\mu\text{mol/L}$ ) and direct bilirubin ( $\mu\text{mol/L}$ ).

- Renal chemistry: creatinine ( $\mu\text{mol/L}$ ) and blood urea nitrogen (BUN) (mmol/L).

- Electrolytes: calcium (mmol/L), chloride (mmol/L), phosphorus (mmol/L), potassium (mmol/L), sodium (mmol/L) and bicarbonates (mmol/L).

- Metabolism parameters: glucose (mmol/L), cholesterol (mmol/L), triglycerides (mmol/L), lipase (IU/L), uric acid ( $\mu\text{mol/L}$ ) and lactate dehydrogenase (LDH) (IU/L).

- Other parameters: albumin (g/L), creatine kinase (CPK) (IU/L), total protein (g/L), alpha fetoprotein (ug/L) only at screening, Alpha-1 Acid Glycoprotein (g/L) only at screening, Beta natriuretic peptide (BNP) and NT-pro-BNP.

**Coagulation** parameters will be listed and grouped as follows:

- Coagulation parameters: prothrombin time (PT) (s), activated partial thromboplastin time (aPTT) (s) and international normalized ratio (INR).

**Urinalysis** parameters will be listed and grouped as follows:

- Planned urinalysis parameters: dipstick determination of pH, specific gravity, glucose, bilirubin, ketones, leukocytes, nitrite, occult blood, protein and urobilinogen.

- Direct microscopy: in case of abnormal urinalysis parameters (in listing only).

**Hormonology** parameters will be listed as follows: FSH (IU/L) and estradiol (pmol/L)

In case a laboratory test result is *censored* (no numeric value is available, but only a verbatim term), the following rules are applied:

- $< x$  or  $> x \rightarrow$  a numeric value will be imputed by a value exceeding the cut-off value with one unit.
- $\leq x$  or  $\geq x \rightarrow$  imputation by  $x$ .

Laboratory values will be graded based on the following toxicity grading scale: The Division of AIDS Table for Grading the Severity of Adult and Pediatric AEs (“DAIDS grading table”, version of November 2014), Appendix F - protocol version 8.0 of the 13rd of September 2016.

Lab values will also be graded based on WHO grading scale, but summary tables will be based on DAIDS grading scale only.

For haematology, blood chemistry, and coagulation, raw data and changes from baseline (Day 1) if applicable will be described by measurement time, for each cohort.

For all lab parameters with toxicity grade, a summary table with the number and percentage of subjects with treatment emergent grade 1-4 and 3+4 will be generated for each cohort for the worst post-baseline value. The same table will be provided by measurement time.

For haematology and blood chemistry, graphs of individual subject values (spaghetti plots) will be generated for each cohort for the following parameters: ALT, AST, alkaline phosphatase, total bilirubin, direct bilirubin, blood urea nitrogen, creatinine, CPK, BNP, haemoglobin, platelets and white blood cells.

A listing of all values of a parameter over time for any parameter with treatment emergent Grade 3 or 4 will be generated. A listing of all values of a parameter over time for any parameter with treatment emergent abnormal values will be also generated.

Values will be listed (raw data and change from baseline) and laboratory abnormal values will be flagged with their toxicity grades and clinical significance information.

For urinalysis, raw data will be described by measurement time, for each cohort.

Urinalysis values will be listed including direct microscopy if any.

Hormonology parameters will be listed only.

For applicable lab parameters, cross-tabulation of the worst toxicity grades versus baseline will be presented, Plots of mean(SE), mean(SE) of change from baseline by cohort over time and Bar graphs of the treatment emergent abnormality by toxicity grade over time for selected laboratory parameters will be plotted.

In determining DAIDS toxicity grades the following rules are applied:

- The worst grades/abnormalities are determined over the whole observational period, including all post-reference scheduled and unscheduled measurements.
- The abnormalities “abnormally low” and “abnormally high” are considered equally important, i.e. if a subject has an “abnormally low” as well as an “abnormally high” post-reference value, both abnormalities are shown in the tables. (This means that the sum of the percentages can be more than 100%)
- If, for a specific test, the grading list provides distinct limits for abnormally low (=hypo) values as well as for abnormally high (=hyper) values, this test should be repeated for hyper and hypo limits separately in cross-tabulations and in the ADaM database.

For the grades, no distinction will be made between test results of samples obtained under fasting and under non-fasting conditions: in case limits under fasting and non-fasting conditions differ, the limits of the conditions (fasting/non-fasting) of scheduled visits as planned in the CTP will always be used, also for samples obtained under a different condition (e.g. samples of withdrawal visits).

Definition treatment-emergent: An abnormality (toxicity grade or abnormality based on normal ranges) will be considered treatment-emergent in a particular phase if it is worse than the reference. If the reference is missing, the abnormality is always considered as treatment-emergent. A shift from “abnormally low” at reference to “abnormally high” post reference (or vice versa) is also treatment-emergent.

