7.9 ALT, AST, and Bilirubin Elevations

Although an AST and ALT elevation of up to Grade 3 is common in chronic HCV infection due to disease activity, treatment-emergent changes from baseline in ALT and AST levels should be carefully evaluated and closely monitored, with unscheduled study visits if needed. Increases in bilirubin (both direct and indirect) have been observed during the first weeks of SMV therapy. These bilirubin elevations are caused by a benign competitive inhibition of biliary transporter systems in hepatocytes. Bilirubin elevations following initiation of SMV therapy are typically not associated with increases in ALT or AST levels and rapidly resolve after completion of SMV treatment. Bilirubin elevations have been observed to a much lesser extent with direct-acting antiviral regimens where SMV is administered without RBV compared to when it is administered with RBV.¹⁶

Management of treatment-emergent AST, ALT and/or bilirubin elevations will take into account the protocol-defined procedures outlined in Table 7-3, [Table 7-4](#), and [Table 7-5](#).

Table 7-3. Treatment-Emergent Grade 1 to Grade 4 ALT or AST Elevation and Grade 1 to Grade 4 Total Bilirubin Elevation

WHO Toxicity Grade	AST or ALT, Ranges	Total Bilirubin, Ranges
Grade 1	≥ 1.25 to $\leq 2.5 \times$ ULN	≥ 1.1 to $\leq 1.5 \times$ ULN
Grade 2	> 2.5 to $\leq 5.0 \times$ ULN	> 1.5 to $\leq 2.5 \times$ ULN
Grade 3	> 5.0 to $\leq 10.0 \times$ ULN	> 2.5 to $\leq 5.0 \times$ ULN
Grade 4	$> 10.0 \times$ ULN	$> 5.0 \times$ ULN

Subjects may continue the intake of study drugs at the investigator's discretion in case of Grade 1 and 2 increases in ALT and/or AST and/or Grade 1, 2 and 3 increases in bilirubin levels. In case of a Grade 3 ALT and/or AST increase or if a Grade 4 ALT and/or AST $\leq 2 \times$ the baseline value, this laboratory abnormality must be judged by the investigator to be either "not related" or "doubtfully related" to the study drugs in order to continue the intake of study drugs, in which case the intake of study drugs may be continued upon agreement with the Sponsor. In subjects who continue the study drugs, close clinical follow up is recommended to monitor for any progressive increases.

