The *Division of AIDS (DAIDS) Table for Grading the Severity of Adult and Pediatric Adverse Events, Version 2.0* consists of parameters, or AEs, with severity grading guidance that are to be used in DAIDS clinical trials for safety data reporting to maintain accuracy and consistency in the evaluation of AEs. The term “severe” is not the same as the term “serious” in classifying AEs. The severity of a specific event describes its intensity, and it is the intensity which is graded. Seriousness, which is not graded, relates to an outcome of an AE and is a regulatory definition.

Clinical sites are encouraged to report parameters in the DAIDS AE grading table as they are written to maintain data consistency across clinical trials. However, since some parameters can be reported with more specificity, clinical sites are encouraged to report parameters that convey additional clinical information. For example, diarrhea could be reported as neonatal diarrhea; seizures, as febrile seizures; and pain, as jaw pain.

The DAIDS AE grading table provides an AE severity grading scale ranging from grades 1 to 5 with descriptions for each AE based on the following general guidelines:

- Grade 1 indicates a mild event
- Grade 2 indicates a moderate event
- Grade 3 indicates a severe event
- Grade 4 indicates a potentially life-threatening event
- Grade 5 indicates death (*Note: This grade is not specifically listed on each page of the grading table*).

Other points to consider include:

- Use parameters defined by age and sex values as applicable.
- Male and female sex are defined as sex at birth.
- Unless noted, laboratory values are for term neonates. Preterm neonates should be assessed using local laboratory normal ranges.
- Where applicable, Standard International (SI) units are included in italics.

Selecting and Reporting a Primary AE Term

When selecting a primary AE term to report, sites should select the term that best describes what occurred to the participant. For example, a participant may present with itching, urticaria, flushing, angioedema of the face, and dyspnea. If the underlying diagnosis is determined to be an acute allergic reaction, sites should report “Acute Allergic Reaction” as the primary AE term.

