Bilirubin Direct Bilirubin¹⁴, High > 28 days of age	NA	NA	> ULN	> ULN with life-threatening consequences (e.g., signs and symptoms of liver failure)
\leq 28 days of age	ULN to \leq 1 mg/dL	> 1 to \leq 1.5 mg/dL	> 1.5 to \leq 2 mg/dL	> 2 mg/dL
Total Bilirubin, High > 28 days of age	1.1 to < 1.6 x ULN	1.6 to < 2.6 x ULN	2.6 to < 5.0 x ULN	\geq 5.0 x ULN
\leq 28 days of age	See Appendix A. Total Bilirubin for Term and Preterm Neonates	See Appendix A. Total Bilirubin for Term and Preterm Neonates	See Appendix A. Total Bilirubin for Term and Preterm Neonates	See Appendix A. Total Bilirubin for Term and Preterm Neonates
Calcium, High (mg/dL; mmol/L) \geq 7 days of age	10.6 to < 11.5 2.65 to < 2.88	11.5 to < 12.5 2.88 to < 3.13	12.5 to < 13.5 3.13 to < 3.38	\geq 13.5 \geq 3.38
< 7 days of age	11.5 to < 12.4 2.88 to < 3.10	12.4 to < 12.9 3.10 to < 3.23	12.9 to < 13.5 3.23 to < 3.38	\geq 13.5 \geq 3.38

¹⁴ Direct bilirubin > 1.5 mg/dL in a participant < 28 days of age should be graded as grade 2, if < 10% of the total bilirubin.

Chemistries

PARAMETER	GRADE 1 MILD	GRADE 2 MODERATE	GRADE 3 SEVERE	GRADE 4 POTENTIALLY LIFE- THREATENING
Calcium (Ionized), High (mg/dL; mmol/L)	> ULN to < 6.0 > ULN to < 1.5	6.0 to < 6.4 1.5 to < 1.6	6.4 to < 7.2 1.6 to < 1.8	≥ 7.2 ≥ 1.8
Calcium, Low (mg/dL; mmol/L) ≥ 7 days of age	7.8 to < 8.4 1.95 to < 2.10	7.0 to < 7.8 1.75 to < 1.95	6.1 to < 7.0 1.53 to < 1.75	< 6.1 < 1.53
< 7 days of age	6.5 to < 7.5 1.63 to < 1.88	6.0 to < 6.5 1.50 to < 1.63	5.50 to < 6.0 1.38 to < 1.50	< 5.50 < 1.38
Calcium (Ionized), Low (mg/dL; mmol/L)	< LLN to 4.0 < LLN to 1.0	3.6 to < 4.0 0.9 to < 1.0	3.2 to < 3.6 0.8 to < 0.9	< 3.2 < 0.8
Cardiac Troponin I, High	NA	NA	NA	Levels consistent with myocardial infarction or unstable angina as defined by the local laboratory
Creatine Kinase, High	3 to < 6 x ULN	6 to < 10 x ULN	10 to < 20 x ULN	≥ 20 x ULN
Creatinine, High	1.1 to 1.3 x ULN	> 1.3 to 1.8 x ULN OR Increase of > 0.3 mg/dL above baseline	> 1.8 to < 3.5 x ULN OR Increase of 1.5 to < 2.0 x above baseline	≥ 3.5 x ULN OR Increase of ≥ 2.0 x above baseline
Creatinine Clearance¹⁵ or eGFR, Low Report only one	NA	< 90 to 60 ml/min or ml/min/1.73 m ² OR 10 to < 30% decrease from baseline	< 60 to 30 ml/min or ml/min/1.73 m ² OR ≥ 30 to < 50% decrease from baseline	< 30 ml/min or ml/min/1.73 m ² OR ≥ 50% decrease from baseline or dialysis needed

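### For direct bilirubin, the DAIDS treatment-emergent tables are in effect binary at ULN: any first rise above it counts as severe, and worsening from a raised baseline is not flagged on value alone

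*SAP*

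**What the plan says.** SAP 8.2 lists "direct bilirubin" among the liver function parameters. On grading it states: "Lab values will also be graded based on WHO grading scale, but summary tables will be based on DAIDS grading scale only". For each parameter that has a toxicity grade, it plans by-cohort counts of treatment-emergent Grades 1-4 and 3+4, for the worst post-baseline value and by measurement time. It also plans a listing triggered by treatment-emergent Grade 3 or 4 values.

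Under the same section, an abnormality "will be considered treatment-emergent in a particular phase if it is worse than the reference". This applies to toxicity grades and to normal-range categories. A missing reference always makes the abnormality treatment-emergent.

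In the adult direct bilirubin row of Protocol Appendix F, Grades 1 and 2 are not applicable and Grade 3 is any value above ULN. Grade 4 begins "> ULN with life-threatening consequences (e.g., signs and symptoms of liver failure". Total bilirubin has four grades by multiples of ULN; its Grade 2, for example, is "1.6 to < 2.6 x ULN". The appendix explains that "Grade 3 indicates a severe event".

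Protocol 7.9 expects a simeprevir effect: "Increases in bilirubin (both direct and indirect) have been observed during the first weeks of SMV therapy". It attributes this to benign inhibition of biliary transporters. Protocol 1.4.1 reports that bilirubin rises in the simeprevir Phase 3 programme were mostly Grade 1 or 2 and involved both fractions.

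**The concern.** A scale that jumps from ungraded to Grade 3 at ULN can mislead in two directions when paired with a rule that counts only a worse grade.

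- **Trivial rises look severe.** A small first excursion above ULN, of the kind the protocol expects with simeprevir, enters the Grade 3 and 3+4 counts. Simeprevir is in every specified cohort except 1b and 4 (SAP 3.1), so any inflation would fall mainly on the simeprevir cohorts.
- **Worsening from a raised baseline is not flagged.** Such baselines are possible. Exclusion criterion 14 (Protocol 4.3) sets a bilirubin limit of 1.5 mg/dL without naming the fraction, sets no separate direct bilirubin limit and allows documented Gilbert's disease. Subjects with Child-Pugh A cirrhosis are also enrolled.

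Laboratory safety is part of the primary endpoint, and Protocol 10.4.2 names the Grade 3 and 4 counts as an output. Protocol 10.8 also plans to pool these safety data with a Phase 2b study to support Phase 3.

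**Working it through.** The plan gives no figure to reproduce here, so the check applies its rules to illustrative values. These values are assumptions, not trial data.

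**Inputs**, with x = value / ULN:

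- DAIDS direct bilirubin (Protocol Appendix F): Grade 0 if x ≤ 1; Grade 3 if x > 1; Grade 4 if x > 1 and life-threatening consequences are recorded.
- DAIDS total bilirubin (Protocol Appendix F): Grade 1 from 1.1 to <1.6; Grade 2 from 1.6 to <2.6; Grade 3 from 2.6 to <5.0; Grade 4 from 5.0.
- Treatment-emergent (SAP 8.2): post-baseline grade > baseline grade.
- Bands proposed under the fix: 0 = ≤1; 1 = >1-1.5; 2 = >1.5-2.5; 3 = >2.5-5; 4 = >5.

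| Baseline → post (x ULN) | Direct, DAIDS | Flagged? | Total at same multiples, DAIDS | Flagged? | Direct, proposed band | Flagged? |
|---|---|---|---|---|---|---|
| 0.8 → 1.05 | 0 → 3 | yes | 0 → 0 | no | 0 → 1 | yes |
| 0.8 → 1.3 | 0 → 3 | yes | 0 → 1 | yes | 0 → 1 | yes |
| 0.8 → 2.0 | 0 → 3 | yes | 0 → 2 | yes | 0 → 2 | yes |
| 0.8 → 6.0 | 0 → 3 | yes | 0 → 4 | yes | 0 → 4 | yes |
| 1.05 → 1.3 | 3 → 3 | no | 0 → 1 | yes | 1 → 1 | no |
| 1.2 → 2.0 | 3 → 3 | no | 1 → 2 | yes | 1 → 2 | yes |
| 1.2 → 3.0 | 3 → 3 | no | 1 → 3 | yes | 1 → 3 | yes |
| 1.2 → 6.0 | 3 → 3 | no | 1 → 4 | yes | 1 → 4 | yes |

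The total bilirubin columns compare the two scales. They do not assume that both measures rise by the same multiple in one subject.

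**Reading the table**

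1. From a normal baseline, 1.05 and 6.0 x ULN receive the same direct bilirubin grade. Grade 3 starts just above 1.0 x ULN for direct and at 2.6 x ULN for total bilirubin.
2. From a baseline above ULN, no numeric rise changes the direct bilirubin grade. On a grid of 600 values from 1.01 to 7.00 x ULN there are 600 × 599 / 2 = 179,700 worsening pairs, and none is flagged.
3. If the Grade 4 qualifier is recorded, 3 → 4 is flagged. A missing baseline is flagged by rule.
4. The normal-range category does not help, because high to high is not worse.

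**The case against.** The strongest reply is that this is one row of a standard scale that the protocol itself mandates, and that the information is not lost. Much of that stands.

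- **DAIDS versus WHO is not the cause.** A reader might blame the choice of DAIDS over WHO. The protocol's WHO grading in Table 7-3 has a column for "Total Bilirubin, Ranges" and none for direct bilirubin, so WHO tables would leave direct bilirubin ungraded. Protocol 10.4.2 also requires DAIDS summaries.
- **Never flagged is too strong.** A reader might infer that worsening from a raised baseline can never be treatment-emergent. Grade 4 and the missing-reference rule are both routes to a flag. The SAP does not say how the clinical qualifier would be attached to a laboratory value, but silence does not make it impossible.
- **Worsening remains visible.** SAP 8.2 plans raw values and changes from baseline by visit, individual plots that name direct bilirubin, and full listings. Total bilirubin has its own four-grade rows, and Tables 7-3 and 7-5 base bilirubin management on it. SAP 8.1 summarises increased-bilirubin events by WHO grade, and the search terms include conjugated bilirubin.
- **Reach is limited.** No pooled hepatic Grade 3/4 count and no significance test is planned. Bar graphs and cross-tabulations cover only selected or applicable parameters, and direct bilirubin is not named for either.
- **Rises may be few.** Protocol 7.9 says bilirubin rises are much less marked when simeprevir is given without ribavirin, as here. Protocol 1.2.1.2 reports no laboratory safety concern as of 6 February 2017.

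What remains is that the categorical by-cohort counts for this analyte do not mean what Grade 3 and treatment-emergent normally convey. Adverse event tables are not a dependable substitute. Under Protocol 7.2.2 an objective finding becomes an event only with symptoms, intervention, discontinuation, added treatment or a serious outcome. The total bilirubin rows help only if the direct rise also moves total bilirubin up a grade. The documents give no normal ranges from which to judge that.

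**Conclusion.** The point holds for direct bilirubin alone. Its treatment-emergent table will in effect count subjects who cross ULN and label them severe. It will not separate small from large rises, and it will not flag further worsening from a raised baseline on numeric value.

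The size cannot be computed. The documents give neither the frequency of direct bilirubin above ULN on treatment nor the number of subjects above ULN at baseline, which could be zero. In a cohort of 20 each subject labelled Grade 3 moves the rate by 1/20 = 5 percentage points; in a cohort of 10, by 10. A reader might want a count such as 2 to 10 of 20, but that is simply 10% to 50% of 20 with the percentages assumed, and nothing in the documents supports them.

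Nor do the documents support a claim that hepatic toxicity as a whole would be overstated or that worsening would be hidden from the report. This is a misleading count within the primary safety endpoint, worth correcting because the correction is cheap. The conclusion assumes that the SAP rules are programmed as written and that Grade 4 is not assigned from the numeric value.

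**What to change.** In SAP 8.2:

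1. Keep the DAIDS direct bilirubin row in the summary tables. Moving it to listings only would conflict with Protocol 10.4.2.
2. Add a by-cohort summary of direct bilirubin by multiples of ULN, for example >1-1.5, >1.5-2.5, >2.5-5 and >5 x ULN. Define treatment-emergent there as a higher band than baseline. The upper cut-points match Table 7-3 for total bilirubin. The lowest band does not, because Table 7-3 Grade 1 starts at 1.1 x ULN.
3. Footnote the DAIDS direct bilirubin Grade 3 and 3+4 rows: Grade 3 begins at any value above ULN, and Grade 4 needs clinical consequences.

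Leave total bilirubin as planned. The cost is one derived variable, one table and one footnote. A rise within a band, such as 1.05 to 1.3 x ULN, would still not be flagged, but no band other than the open top one can conceal a large rise.

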### 8.3 Other safety parameters

#### 8.3.1 Vital signs data

Blood pressures (diastolic [DBP] and systolic [SBP]; mmHg), respiratory rate (breaths/min), body temperature (°C) and pulse rate (bpm) will be measured (see section [12.1](#)) for each cohort at the screening visit, Day 1, Week 1 and then once a week thereafter.

Raw data and changes from baseline (Day 1 pre-dose) will be described by measurement time, for each cohort.

A summary table with the number and percentage of subjects with PCSA values (defined in section [12.2](#)) will be generated by measurement time, for each cohort.

A specific listing of all values of a parameter over time for any parameter with PCSA values with clinical significance information will be generated.

Pulse rate, DBP, and SBP are classified in the following abnormality codes:

	Pulse (bpm)	DBP (mmHg)	SBP (mmHg)
Abnormally low	≤ 50	≤ 50	≤ 90
Abnormally high	≥ 120	-	-
Grade 1 or mild	-	> 90 - < 100	> 140 - < 160
Grade 2 or moderate	-	≥ 100 - < 110	≥ 160 - < 180
Grade 3 or severe	-	≥ 110	≥ 180

A summary table with the number and percentage of subjects with abnormal values (as defined above) will be generated for each cohort for the worst post-baseline value. The same table will be provided by measurement time.

A specific listing of all values of a parameter over time for any parameter with abnormal values with clinical significance information will be generated.

Values (raw data and changes from baseline) will be listed and PCSA and abnormal values will be flagged with clinical significance information.

Graph of mean (SE) by cohort over time will be plotted.

In determining the abnormalities, the following rules are applied:

- Worst grades/abnormalities are determined over the whole observational period, including post-baseline scheduled and unscheduled measurements.

- The abnormalities ‘abnormally low’ and ‘abnormally high’/grades are considered equally important, i.e. if a subject has an ‘abnormally low’ as well as an ‘abnormally high’ or graded post-baseline value, both abnormalities are shown in the tables. (This means that the sum of the percentages can be more than 100%.)

Definition treatment-emergent:

An abnormality will be considered treatment-emergent if it is worse than the baseline. If the baseline is missing, the abnormality is always considered as treatment-emergent. A shift from ‘abnormally low’ at baseline to ‘abnormally high’ or ‘grade 1’ or ‘grade 2’ or ‘grade 3’ post baseline (or vice versa) is also treatment-emergent.

